### **Hypothesized Effect Size for Intervention on Main Patient-Centered Outcome**

Based on prior studies of chronic medications, we hypothesize that we will find a decrease of 5-9% in the PDC for controller medications after switching to HSA-HDHPs without PDLs relative to traditional plans, and an increase in the number of fills of 1-4% for those who switch to HSA-HDHPs with PDLs relative to HSA-HDHPs without PDLs.

### **Sample Size and Power**

**Aim 1:** We will conduct qualitative interviews with approximately 60 patients or parents or patients.

**Aims 2-4:** We estimate that there are 1,695 patients with asthma eligible for our study in 2004 in our dataset (12% of HSA-HDHP members), increasing to 2,449 by 2011 (17% of HSA-HDHP members). Projecting current trends, we expect a total of 22,500 HSA-HDHP members with asthma by 2017. Preliminary numbers suggest a third of the cohort will be children under age 18. Based on detailed estimates from our health insurance partners, ~19% of HSA-HDHP members have a PDL. We will have an abundant number of traditional plan members, more than seven times the number in HSA-

HDHPs. Table 3 displays power calculations for pairs of regression models we plan to run for three primary outcomes: controller medication adherence (PDC) (Aims 2-3), and adverse clinical outcomes (rate of asthma-related ED visits or hospitalizations) (Aims 2-3), and OOP costs (Aim 4), both overall and for stratified analyses by adult/child (power calculations for children are displayed, as they are the smaller group). Power calculations, which assume 80% power and 0.05 alpha level, were performed using PASS software.

**Table 3: Power calculations**

| Contrast of Interest                                  |                                 | Least detectable absolute difference |          |
|---|---------------------------------|--------------------------------------|----------|
| Intervention Group                                    | Control                         | Overall                              | Children |
| Controller medication adherence (PDC)*         |                                 |                                      |          |
| HSA-HDHP with PDL (n=4,222)                           | HSA-HDHP without PDL (n=16,888) | 2.0%                                 | 3.5%     |
| HSA-HDHP without PDL (n=18,000)                       | Traditional plan (n=72,000)     | 1.0%                                 | 1.7%     |
| Asthma related ED visits or hospitalizations** |                                 |                                      |          |
| HSA-HDHP with PDL (n=4,222)                           | HSA-HDHP without PDL (n=16,888) | 1.2%                                 | 2.0%     |
| HSA-HDHP without PDL (n=18,000)                       | Traditional plan (n=72,000)     | 0.6%                                 | 1.0%     |
| OOP costs***                                   |                                 |                                      |          |
| HSA-HDHP with PDL (n=4,222)                           | HSA-HDHP without PDL (n=16,888) | \$47                                 | \$80     |
| HSA-HDHP without PDL (n=18,000)                       | Traditional plan (n=72,000)     | \$23                                 | \$40     |

\*Baseline rate estimated at 46% \*\* Baseline rate estimated at 8.4 per 100 patients with asthma \*\*\*Baseline OOP costs estimated at \$740 based on data from current studies in the same data set.

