### Overview of Study Protocol (RQ-2)

This project will employ both qualitative and quantitative methods, based on theoretical models adopted from Levy and Meltzer's model of the effect of health insurance on health outcomes, and known causal pathways linking asthma controller medication adherence to reductions in short-term complications.

In Aim 1, we will conduct in-depth qualitative interviews with approximately 60 commercially-insured patients with asthma or parents of children with asthma who have HDHPs with and without PDLs, or traditional plans. These telephone interviews will explore how patients and their families understand and navigate their HDHP and make health care decisions and trade-offs when faced with out-of-pocket costs. Insights gained from these interviews will shape and inform the quantitative analyses in Aims 2-4.

[figure not shown]
In Aims 2-4, we will maximize internal validity, reduce selection bias, and address causal inference standards by employing cutting-edge study designs and analytic methods that we have used in our prior work (CI-1,4): (1) ITS with comparison series design, the most rigorous quasi-experimental design for causal inference; (2) a population whose employers offer only a single health plan type, minimizing self-selection bias; (3) matching groups on the functional form of the baseline trend, recently shown to approximate estimates from RCTs; and (4) a rigorous and validated two-level propensity score matching approach that matches on both individual and employer baseline characteristics and includes family-level characteristics. We will follow individuals and families with asthma for 1 year before and up to 3 years after an index date when they are required to switch to HSA-HDHPs with or without PDLs, or to remain in HSA-HDHPs without PDLs or remain in traditional plans. We will identify two primary intervention groups of interest: 1) patients with asthma switched by employers from traditional plans to HSA-HDHPs *without* PDLs; and 2) patients switched from HSA-HDHPs *without* PDLs to HSA-HDHPs *with* PDLs. Patients in each group will be propensity-matched to patients with asthma who remain by employer choice in the same plan.

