### **Description of Comparators (RQ-5)**

This project will assess the impact of the "intervention" of being switched to an HSA-HDHP with a PDL, relative to a control group that was not switched and remained in an HSA-HDHP, and of being switched to an HSA-HDHP without a PDL relative to a control group that was not switched and remained in a traditional plan. Comparator groups include:

**HSA-HDHP with PDL:** enrollment in an HSA-qualified HDHP with a PDL that exempts asthma controller and rescue medications from the deductible, after being switched by an employer from an HSA-HDHP without PDL or from a traditional plan. There is limited data on the effectiveness of HSA-HDHPs with PDLs on asthma outcomes, despite an estimated prevalence of 19% among HSA-HDHP enrollees based on the national health plan to be studied. Other VBID programs have shown modest increases in adherence to chronic medications.

**HSA-HDHP without PDL:** enrollment in an HSA-qualified HDHP without a PDL, after being switched by an employer from a traditional plan. Those who enroll in HSA-HDHPs without PDLs and do not switch will also be used as a control group for those who switch from HSA-HDHPs without PDLs to HSA-HDHPs with PDLs. Evidence in adult populations suggest a reduction in adherence to asthma medications for those enrolling in HSA-HDHPs without PDLs. In 2015, the prevalence of HSA-HDHPs among covered workers was 15%.

**Traditional plan:** enrollment in a plan with no or a low (<\$500) deductible through an employer who offers only one plan. Fifty-four percent of covered workers have traditional plans, with a baseline proportion of days covered (PDC) for asthma medications of 46%.

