For **Aims 2-4**, the study population will be drawn from 14 years of data from a large U.S. commercial health plan with membership in all 50 states and annual enrollment of ~30 million members. The eligible population will consist of adults aged 18-64 years and children aged 4-17 years with asthma in a baseline year while insured in a traditional plan; all subjects must have continuous insurance coverage with pharmacy benefits for at least 24 consecutive months. Study subjects must have spent a year in a traditional health plan with no or low deductibles prior to the switch to an HSA-HDHP without a PDL, or have spent a year in an HSA-HDHP without a PDL before switching to an HSA-HDHP with PDL, and then remain enrolled for at least one-year post-switch. Control group members spend a year in a traditional plan or a HSA-HDHP without PDL then remain that plan for at least another 12 months. As study groups for secondary analyses, we will also identify enrollees switching from traditional plans to HSA-HDHPs with PDLs for comparison with those remaining in traditional plans. We will also identify enrollees with other plan types, not just HSA-HDHPs, which appear to have PDLs in that they have lower cost-sharing for asthma medications compared to other non-preventive medications. Based on preliminary findings from qualitative interviews as part of Aim 1 of the project, we have learned the cost of asthma medications is a problem not only for enrollees in HSA-HDHPs but in other types of HDHPs and in traditional plans with low deductibles as well, so we will also identify enrollees who are switched from having no PDL to having a PDL. Each of these groups will be matched with controls who start in the same type of plan and remain in that type of plan without gaining a PDL.

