Eligible employers are those that offer only one plan type in a given benefit year: 1) traditional HMO/PPO/POS plans (deductibles  $<\$1000$ , copayments of  $<\$50$  for most services, tiered copayments for medicines); 2) HSA-HDHPs without PDLs; or 3) HSA-HDHPs with PDLs. We will select “full-replacement” employers that replace a traditional plan with an HSA-HDHP without PDL, or replace an HSA-HDHP without PDL with an HSA-HDHP with PDL, for all employees at a given point in time; matched comparison employers will include those that keep all employees in their prior plan. Including only full-replacement employers is a key strategy used in multiple previous studies to reduce member self-selection bias. The index dates for HSA-HDHP enrollees will be the dates of the employer-mandated plan switch. Matched controls will have contemporaneous enrollment in traditional plans also mandated by their employers; index dates will be assigned to be the same as matched intervention enrollees. We will also include matched controls who remain in HSA-HDHPs without PDLs. To reduce bias due to dropout, we will censor both HDHP and control patients together when either one drops out, and weight the remaining population to retain its baseline demographic and clinical profile. We estimate that there will be 621,481 adults and 310,741 children with asthma from 2004-2017 who will meet our inclusion criteria: 18,000 asthma patients in HSA-HDHPs without PDLs, 4,222 in HSA-HDHPs with PDLs, and 910,000 in traditional plans.

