*Hypothesis (see Figure 2): Enrollees with asthma in HSA-HDHPs without PDLs will have worse adherence to controller medications, greater need for rescue medications, and higher rates of asthma-related ED visits and hospitalizations, with widening of income and racial/ethnic disparities; the addition of a PDL will improve use of controllers and rescue medications, reduce ED and hospitalization rates, and lessen disparities.*

Analyses will compare changes in outcomes from baseline to up to three years of follow-up among 1) asthma patients switched to HSA-HDHPs without PDLs from traditional plans vs. matched patients whose employers remain in traditional plans; and 2) patients switched to HSA-HDHPs with PDLs from traditional plans vs. matched controls remaining in HSA-HDHPs without PDLs. Sensitivity analyses will compare patients switched to HSA-HDHPs with PDLs from traditional plans vs. those who remain in traditional plans to examine the combined impact of both increasing the deductible and gaining a PDL. We will use separate regression models to compare year-to-year changes for each intervention group relative to its matched control group, rather than including all patients in a single model with multiple interaction terms. For secondary analyses of enrollees in the larger set of plan types that include PDLs, we will compare enrollees who are switched from plans with no PDL to plans with a PDL vs. those who remain in plans without a PDL. These analyses will match and adjust for different baseline plan types and deductible levels.

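### The Aim 2 analysis plan gives the primary PDL contrast a different baseline plan from the rest of the protocol, and Table 3's counts for that contrast are optimistic and fit neither definition clearly

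*Combined protocol and SAP*

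**What the plan says.** **Who enters the contrast.** The Overview of Study Protocol names as its second primary intervention group "patients switched from HSA-HDHPs *without* PDLs to HSA-HDHPs *with* PDLs", with each group matched to patients who stay in the same plan. Specific Aims describes the same contrast. Study Population requires a year in an HSA-HDHP without PDL before the switch and selects employers making that replacement. Predictors and Covariates matches the groups on characteristics measured while both were in the same type of plan.

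Study Population makes the other route secondary: "As study groups for secondary analyses, we will also identify enrollees switching from traditional plans to HSA-HDHPs with PDLs", compared with those remaining in traditional plans. Description of Comparators defines the PDL group as enrolled "after being switched by an employer from an HSA-HDHP without PDL or from a traditional plan". The Aim 2 analysis plan gives its second main comparison as "patients switched to HSA-HDHPs with PDLs from traditional plans vs. matched controls remaining in HSA-HDHPs without PDLs".

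**How many.** Study Population expects "18,000 asthma patients in HSA-HDHPs without PDLs, 4,222 in HSA-HDHPs with PDLs, and 910,000 in traditional plans". Sample Size and Power says that about "19% of HSA-HDHP members have a PDL". On eligibility, "all subjects must have continuous insurance coverage with pharmacy benefits for at least 24 consecutive months".

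**What is detectable.** Table 3 sets 4,222 PDL patients against "HSA-HDHP without PDL (n=16,888"), and 18,000 no-PDL patients against 72,000 in traditional plans. The least detectable absolute PDC differences are 2.0% and 1.0% overall, and 3.5% and 1.7% for children. The text gives 80% power and alpha 0.05 without sidedness. The only PDC input is a 46% baseline. The Hypothesized Effect Size section puts the PDL effect at 1-4% in number of fills.

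**The concern.** The PDL contrast is the study's central question. If the Aim 2 sentence is programmed as written, cases move from copayments to a high deductible with a PDL, while controls have a high deductible throughout. A difference-in-differences on those groups does not isolate the PDL. A baseline match in the same type of plan, which the protocol relies on for causal inference, would not be possible.

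The planning figures do not help the reader decide which group is meant. They appear to treat all PDL patients as eligible cases and almost all no-PDL patients as matched controls. If the real counts are smaller, the detectable difference rises. With the variance inputs missing and the hypothesis on another scale, a null PDL result could not be placed against what the study expected to find.

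**Working it through.** **1. Definitions side by side.**
- Specific Aims, Overview, and the switch and employer criteria in Study Population: no-PDL to PDL, against no-PDL stayers.
- Predictors and Covariates: both groups in the same type of plan at baseline.
- Aim 3 analysis: PDL against remaining in no-PDL.
- Study Population, secondary groups: traditional to PDL, against traditional stayers.
- Aim 2 analysis, second main comparison: traditional to PDL, against no-PDL stayers.

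Only the last pairs groups with different baseline plans. One general eligibility sentence in Study Population also places everyone in a traditional plan at baseline, but the next sentences give the two routes separately.

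**2. Counts.**
- 18,000 + 4,222 + 910,000 = 932,222 = 621,481 + 310,741 (adults plus children in Study Population), so 18,000 is the whole no-PDL group.
- 4,222 / (18,000 + 4,222) = 0.190, which matches the stated prevalence.
- 4 × 4,222 = 16,888, and 16,888 / 18,000 = 0.938.
- A patient serving in both contrasts needs 12 months in a traditional plan, 12 in no-PDL (follow-up for one contrast, baseline for the other) and 12 more in no-PDL: 36 months, against 24 required.
- Table 4 total: 3,420 + 12,059 + 90,170 + 5,515 = 111,164 = 4,222 + 16,888 + 18,000 + 72,000 + 54 interviews. It therefore counts 18,000 + 16,888 = 34,888 no-PDL patients.

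**3. Table 3's 2.0%.** Detectable difference = k × SD × sqrt(1/n1 + 1/n2), with k = 2.8016 two-sided or 2.4865 one-sided. For the PDL row the square root is 0.017207.
- Treating 46% as a proportion, SD = sqrt(0.46 × 0.54) = 0.498. This gives 2.40 points two-sided and 2.13 one-sided, so the printed 2.0 is not reproduced.
- SDs implied by the printed 2.0, 1.0, 3.5 and 1.7 (children taken as one third of n): 0.415, 0.428, 0.419, 0.420 two-sided; 0.467, 0.483, 0.472, 0.474 one-sided.
- Within rounding, one SD of about 0.42 (two-sided) or 0.47 (one-sided) fits all four cells.

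**4. Sidedness.** ED visits or hospitalizations, two-proportion test of a fall from 8.4%, in percentage points:

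| | PDL all | PDL children | no-PDL all | no-PDL children |
|---|---|---|---|---|
| Printed | 1.2 | 2.0 | 0.6 | 1.0 |
| One-sided 5% | 1.16 | 1.96 | 0.57 | 0.97 |
| Two-sided 5% | 1.30 | 2.20 | 0.64 | 1.10 |

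All four cells match the one-sided test; one matches the two-sided test.

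**5. Pre-post correlation.** A change score has SD × sqrt(2(1 − ρ)). With SD 0.42, two-sided, at the printed counts, the detectable difference is 2.9 points at ρ = 0, 2.0 at 0.5 and 1.6 at 0.7 (the ρ values are assumptions).

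**6. Power, taking 2.0 at face value.** SE = 2.0/2.8016 = 0.714 two-sided, or 2.0/2.4865 = 0.804 one-sided.

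| True PDC difference (points) | Two-sided | One-sided |
|---|---|---|
| 0.46 | 10% | 14% |
| 1 | 29% | 34% |
| 1.84 | 73% | 74% |
| 2 | 80% | 80% |
| 4 | >99% | >99% |

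The rows 0.46 and 1.84 are 1% and 4% of 46, assuming that a relative change in fills equals a relative change in PDC.

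**7. Illustrations only.** Scaling 2.0 by sqrt(1/n1 + 1/n2): controls at 1:2 give 2.2, and at 1:1 2.5. Half the cases eligible at 1:4 gives 2.8, a quarter 4.0. The documents give no such shares. The shortfalls partly offset each other: half the cases need 8,444 controls, 47% of the pool.

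**The case against.** The strongest reply is that the intended contrast is clear. Several sections agree, and the Aim 2 phrase is an isolated slip. Description of Comparators need not conflict, because it can be read as covering both the primary group and the secondary one. This stands, and it narrows the conflict to the Aim 2 wording. That wording is nevertheless the one an analyst would program from.

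On counts, the plan says the 4,222 and 18,000 meet the inclusion criteria, and a projection from prevalence is normal planning. The 16,888 fits within 18,000. A reader might infer that using the same 18,000 in both contrasts is impossible. The documents do not support that: Description of Comparators lets no-PDL patients who do not switch serve as controls, and follow-up of up to three years leaves room for 36 months. Table 4's 34,888 is what counting by contrast would give. What remains is that 93.8% must be matched 1:4, contemporaneously, within a caliper and employer quartile. Matched patients are then censored together, and no loss is shown.

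On power, a reader might infer that 2.0% is an arithmetic error, or that 2.4% is an upper limit. Neither follows. PDC need not be binary, the four cells agree with one SD, and the model used in PASS is not reported. The 2.4% applies to a single-period comparison of independent patients, not to a pre-post design, where step 5 allows values on either side of 2.0. Likewise, the ED match suggests a one-sided test but does not prove it: a two-sided test with a smaller, unstated variance could also fit. Finally, a plan need not power the bottom of its hypothesised range, and Table 3 prints 2.0% openly.

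**Conclusion.** The point holds as an inconsistency in the definition of the primary PDL contrast, with planning counts that do not resolve it. Followed literally, the Aim 2 sentence would confound the PDL effect with the change in deductible.

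On counts, 2.0% is optimistic: it needs 93.8% of the no-PDL pool as controls, uses the whole pool again as cases, and shows no allowance for match failure or joint censoring. How optimistic cannot be said without a recount. Calling 2.0% a best case overall would go too far, because a strong pre-post correlation or smaller SD would lower it.

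Read as absolute PDC points, the upper part of the 1-4% hypothesis is well covered and the part below 2 points is not (29% or 34% power at 1 point). Read as relative to 46%, the whole range falls below 2.0 points, with about 10-73% (two-sided) or 14-74% (one-sided) power. These figures take the printed 2.0% at face value, and the relative reading rests on equating fills with PDC. The missing SD, correlation and sidedness are a reporting gap and do not show that 2.0% is wrong.

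**What to change.** - Correct the Aim 2 comparison so that the primary PDL contrast is no-PDL to PDL against no-PDL stayers, as in the Overview, Study Population and matching text. Keep the traditional-plan route as the secondary analysis against traditional-plan controls.
- Recount eligible no-PDL-to-PDL switchers (12 + 12 months) and no-PDL stayers at matching index dates. State the expected match rate and whether a patient may serve in both contrasts, and use a matching ratio the pool supports.
- Restate Table 3, including the children column, and Table 4 on those counts, giving SD, pre-post correlation and sidedness. If the ED/hospitalization rows were one-sided, restate them two-sided or say so.
- Express the PDL hypothesis in PDC points beside the restated detectable difference.

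The wording change costs almost nothing. The rest is a recount in the claims data, which depends on the update through 2017 and on the PDL-access data the health plan will supply. The restated figures will probably be less favourable. No extra enrolment is needed.

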### Generalizability and Limitations

This study has several limitations. We include in our sample only members offered no choice in health plan selection (exogenous insurance choice). By doing so, we limit generalizability but minimize individual-level selection bias, the major threat to internal validity. Employer selection is still possible, but we minimize this via the two-stage propensity score matching approach. Propensity score matching cannot control for selection on unobserved characteristics, but our planned approach of matching on the baseline trend of outcomes of interest approximates the estimates of randomized controlled trials. Dropout is a problem in longitudinal studies in insured populations. In our analyses, we will track and document drop out from disenrollment and changing plans, and will compare baseline pre-index characteristics of members who have one, two or three years of follow up. Furthermore, we will censor propensity-matched members of our study and comparison groups together if one drops out, and adjust analyses by weighting the members present during a given period of interest based on the baseline distributions of their demographic and health characteristics. If drop out in the third year of follow-up ends up being substantial in the proposed study population, we will limit the follow-up period to 2 years.

There are multiple factors that affect adherence to asthma medications and asthma outcomes in addition to insurance type and cost barriers. We are able to measure many of these factors using claims (e.g. baseline disease severity, age, gender, income, race/ethnicity) but not others (e.g. attitudes, provider factors, competing demands). Claims data also do not allow measurement of important asthma outcomes such as symptom days, missed school/work days, or lung function. The Aim 1 qualitative study will be able to contribute these additional dimensions of non-financial barriers to adherence and asthma outcomes, however. Despite its limitations, claims data permit population-level measurement of important and commonly used downstream indicators of asthma complications such as asthma-related ED visits and hospitalizations which we have experience measuring in our prior asthma studies. The use of geocoding and surname analysis limits our ability to determine member race/ethnicity at the individual level, but provide excellent population-level estimates when used together. We will assess the degree of missingness for these fields in our study, but do not anticipate that it will be problematic given that annual missingness of geocoded SES variables in the study team's prior work using this data source has been less than 1% (MD-1).

Sharing of asthma medications within a family may affect the accuracy of measurement of an individual's medication use based on claims data. However, only 16% of children share or borrow asthma medications, usually bronchodilators. Unlike other studies of cost-sharing and medication use in the literature, our study can capture this effect by measuring family-level medication use and OOP costs. Utilization of medications and other health services in HSA-HDHPs may be affected by the amount of funds in a member's HSA, which can be used to pay deductible costs. Data on HSA balances is not available for all members, however.

Because our interest is assessing clinically relevant effects of an economic intervention, the proposed project does not examine the impact of HSA-HDHPs and PDLs on total costs to employers or the health care system. The impact of HDHPs with PDLs on total costs is important to the decision making of employers and payers, and while beyond the scope of this project, our findings will inform future studies to address this topic using datasets with premium and full cost data.

Prior studies on inhaled asthma rescue medications have found that utilization of these medications is relatively inelastic to price changes, raising the possibility of a “no effect” study. In our study that showed no significant impact on inhaler use from an increase in co-payment, we did not include HDHPs, so the cost increase was not large. In the study by Jena et al, which found a modest decrease in inhaler use with increased out-of-pocket costs, the increases in cost-sharing took the form of both co-payments and deductibles. It is possible that the larger cost-sharing changes associated with HSA-HDHPs and PDLs (ranging from \$0 in PDLs to \$140-\$307 for some inhaled steroids and \$30-60 for albuterol inhalers) could have a larger impact on medication use. Studying the impact of HSA-HDHPs and PDLs with respect to asthma rescue inhalers will still be important even if our study finds no effect on inhaler utilization, as there are likely to be significant changes in out-of-pocket costs for rescue inhaler medications even if use is unchanged. The cost of asthma medications can cause financial burden for families (e.g. having to borrow money or cut back on other necessities), so studying the impact of HSA-HDHPs and PDLs on out-of-pocket costs for asthma rescue inhalers is important even if the utilization analyses produce a “no effect” study.

